### 7. RESEARCH QUESTION AND OBJECTIVE(S)

Following the initiation of CAB+RPV LA regimen among people living with HIV (PLWH), the study will aim to assess effectiveness, discontinuation, and resistance over 24-months of follow-up period in approximately 1000 participants.

The specific objectives are to:

- 1. Describe study population initiating CAB+RPV LA regimen, by baseline demographic and clinical characteristics
- 2. Assess adherence, durability and discontinuation for PLWH starting CAB+RPV LA regimen
  - Proportion of participants discontinuing the CAB+RPV LA regimen and lost to follow-up will be assessed.
    - Reasons for discontinuation will be assessed.
  - Non adherence to dosing schedule will be assessed by
    - a. Estimating the number of participants that missed one or more consecutive injections without taking daily oral bridging therapy or any other oral ARV regimen while not on CAB+RPV LA regimen and mean and median number of injections missed during a 12-month period
    - b. Estimating the number of participants who received the injections seven or more days later than their scheduled injection visit and median duration of delayed injections
- 3. Assess the clinical effectiveness (i.e. proportion of participants experiencing virologic failure) among PLWH who initiate CAB+RPV LA regimen and had suppressed viral load (VL <50 copies/mL) at regimen initiation
  - Estimate the proportion of participants with virologic failure, during the first 6 months after initiation of CAB+RPV LA regimen
  - Estimate the proportion of participants with virologic failure at 6, 12 and 24 months after initiation of CAB+RPV LA regimen
- 4. Monitor for resistance in case of VF while on CAB+RPV LA or after switching to a subsequent ARV regimen among individuals who switched off CAB+RPV LA regimen for any reason
  - Describe the ARV regimen participants are switched to after discontinuation of CAB+RPV LA regimen
  - Describe virologic outcomes at 12, 24, 36 and 48 months after discontinuation of CAB+RPV LA regimen
  - Monitor for virologic failure and resistance during the 48 months following the switch
    - Resistance test to be done for all participants with virologic failure during the follow-up period

 HIV subtype test to be done for participants with virologic failure during the follow-up period, if subtype data is not available

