#### 8.7. Data analysis

All enrolled participants who receive at least one dose of the CAB+RPV LA regimen will be included in the analysis. Participants who are prescribed but never receive a dose of CAB+RPV LA regimen will be excluded from the analysis. Study results will be stratified by the regimen used (Q4/Monthly dosing vs Q8/Every 2 month dosing). Further, study results for co-infected patients with hepatitis B or C will be presented separately. All continuous variables will be summarized using the following descriptive statistics: n (non-missing sample size), mean, standard deviation, 1st quartile, median, 3rd quartile, maximum and minimum. The frequency and percentages (based on the non-missing sample size) of observed levels will be reported for all categorical variables. Data will be analyzed using SAS®, SPSS® or STATA®.

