# AIM 2. Assess adherence, durability and discontinuation for PLWH starting CAB+RPV LA regimen

The proportion of study participants discontinuing the regimen will be assessed at 6, 12-and 24-months using the Kaplan-Meier method. The two-sided 95% confidence intervals of the proportions will be calculated with Kalbfleisch and Prentice's formula. Time to event will be defined as the time between the date of the initiation of CAB+RPV LA regimen and the date of discontinuation of CAB+RPV LA regimen. Death, cause of death where available and lost to follow-up will be excluded from this analysis but will be tabulated and reported separately. Follow-up will be censored at the analysis time point. The estimated median time to discontinuation will be calculated with the two-sided 95% associated confidence interval. Reasons for discontinuation will be given and frequencies and percentages will be reported. Number of individuals that experience blips  $\geq$ 50 to <200 copies/mL will be tabulated along with the number of individuals that have CVF and remain on regimen. Kaplan Meier curves will be plotted with the number of participants at risk at baseline, 6, 12, and 24-month.

The number and proportion and the two-sided 95% associated confidence interval of participants that missed one or more consecutive injections without taking daily oral bridging therapy or any other oral ARV regimen while not on CAB+RPV LA regimen will be calculated. The proportion will be estimated by the number of individuals who missed one or more consecutive injections divided by the total number of study participants in the analysis. The mean and median number of injections missed during a 12-month period will be described by median, 1st quartile, and 3rd quartile.

The number and proportion and the two-sided 95% confidence interval of proportion of individuals who received the injections seven or more days later than their scheduled

injection visit will be calculated. The proportion will be estimated by the number of individuals who received the injections seven or more days later than their scheduled injection visit divided by the total number of study participants in the analysis. The duration of delayed injections will be described by median, 1st quartile, and 3rd quartile.

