# 11. PLANS FOR DISSEMINATING AND COMMUNICATING STUDY RESULTS

#### 11.1. Milestones

This study-specific protocol will be submitted by 31 December 2020 for the EMA's review and endorsement. The study will start only after the protocol is approved by the EMA, and CAB LA and/or RPV LA is registered and commercially available in the relevant countries and is expected to continue through 2026 or later. Annual interim reports with cumulative data will be submitted and a final report is expected to be submitted in March 2027.

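### The late- and missed-injection proportions have no fixed horizon and no adjustment for injections due, so they mix adherence with opportunity

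*Protocol*

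**What the plan says.** Objective 2 (protocol Section 7) covers adherence to the dosing schedule. For late injections the target is "Estimating the number of participants who received the injections seven or more days later than their scheduled injection visit", together with the median delay. For missed injections it is the number of participants with at least one uncovered miss, together with the "mean and median number of injections missed during a 12-month period".

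Section 8.7, AIM 2, turns these into formulas. The missed-injection proportion is the "number of individuals who missed one or more consecutive injections divided by the total number of study participants in the analysis". The late-injection proportion has the same base: persons late for a "scheduled injection visit divided by the total number of study participants in the analysis". Each gets a two-sided 95% confidence interval. Neither has a time point, a censoring rule or a count of injections due.

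The analysis set is set out at the start of Section 8.7: "All enrolled participants who receive at least one dose of the CAB+RPV LA regimen will be included in the analysis". Length of follow-up plays no part in it. The same paragraph stratifies study results by monthly or 2-monthly dosing. Section 11.1 adds: "Annual interim reports with cumulative data will be submitted".

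Other time-dependent outcomes are handled differently. Discontinuation (AIM 2) and virologic failure (AIM 3) use Kaplan-Meier methods. The section on associated factors models non-adherence by Cox regression.

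**The concern.** A person-level proportion of this kind grows with the number of chances each person has had. Two participants with the same habits score differently if one was due 6 injections and the other 24. Three consequences follow from the formula as written.

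- **Over calendar time.** At each annual report the cohort will hold a mixture of short and long follow-up. As follow-up matures the proportion goes up, even if the chance that a given injection is late never changes. A reader of successive cumulative reports could take that for worsening adherence.
- **Between strata.** Monthly dosing gives about twice the opportunities of 2-monthly dosing over the same period. Stratifying keeps the two figures apart but does not make them comparable.
- **Early leavers.** Someone who discontinues after a few punctual injections stays in the denominator as a person without the event.

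Adherence to dosing visits is part of objective 2, and Section 6.2 makes it central to the study's rationale. The protocol fixes the denominator itself, so this is not a detail it has left open for the SAP.

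**Working it through.** The protocol states no adherence rate, so there is no planned adherence figure to reproduce. The nearest stated figures are the discontinuation limits in Table 3 (Section 8.4). Exact Clopper-Pearson limits at n = 1000 reproduce them: 0.064-0.099 at 8% and 0.138-0.184 at 16%. Table 3 is used below only for its range of discontinuation rates.

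**Inputs**
- Follow-up of 24 months: Section 8.5.
- Discontinuation of 8% to 16%: Section 8.4, Table 3.
- Injections due, k: assumed from the interval names, ignoring initiation injections. About 24 monthly and about 12 2-monthly over 24 months.
- Chance q that a given injection is late (or missed): assumed, not in the documents. Range 1%, 2%, 5%; independent and equal for everyone.

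**Step 1. Effect of injections due.** Ever-late proportion = 1 - (1 - q)^k.

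| q | k = 6 | k = 12 | k = 24 | ratio, 24 to 12 |
|---|---|---|---|---|
| 1% | 5.9% | 11.4% | 21.4% | 1.9 |
| 2% | 11.4% | 21.5% | 38.4% | 1.8 |
| 5% | 26.5% | 46.0% | 70.8% | 1.5 |

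At q = 2%, for example, 1 - 0.98^24 = 0.384 and 1 - 0.98^12 = 0.215. For monthly dosing the three columns are 6, 12 and 24 months of follow-up. Late injections divided by injections due would equal q in every cell.

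**Step 2. Mixed follow-up at an interim.** Take monthly dosing, q = 2%, and follow-up spread evenly over 0 to 24 months (an assumption). The mean of 1 - 0.98^k over k = 0, ..., 24 is 20.7%, against 38.4% once everyone has 24 months. Leaving out k = 0 gives 21.6%, so participants with nothing yet due are not driving the result.

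**Step 3. Final analysis.** Let a fraction d discontinue evenly over 24 months. The crude proportion is (1 - d) × full + d × average, where the average runs over k = 0 to 23 (monthly) or 0 to 11 (2-monthly). At q = 2%:

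- Monthly, full 0.384, average 0.200. With d = 0.08: 0.92 × 0.384 + 0.08 × 0.200 = 36.9%. With d = 0.16: 35.5%.
- 2-monthly, full 0.215, average 0.103. With d = 0.08: 20.6%. With d = 0.16: 19.7%.

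Unequal follow-up moves the final monthly figure by about 1.5 to 3 percentage points, against about 18 points in Step 2.

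**Step 4. Clustering within persons.** If some people are habitually late, events concentrate in fewer people. A beta-binomial model with mean 2% and assumed within-person correlation ρ gives 1 - B(a, b + k)/B(a, b), where a = 0.02(1 - ρ)/ρ and b = 0.98(1 - ρ)/ρ.

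| ρ | k = 6 | k = 12 | k = 24 | ratio, 24 to 12 |
|---|---|---|---|---|
| 0 | 11.4% | 21.5% | 38.4% | 1.8 |
| 0.1 | 9.2% | 14.7% | 21.6% | 1.5 |
| 0.2 | 7.7% | 11.3% | 15.2% | 1.3 |

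Clustering shrinks the contrast but does not remove it.

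**The case against.** A reader might infer that the reported figure reflects dosing interval and follow-up rather than adherence. The documents do not support that. At a fixed 24 months under monthly dosing, Step 1 runs from 21.4% to 70.8% as q goes from 1% to 5%, so the measure responds strongly to adherence. The share of people ever late is also a legitimate descriptive quantity, and Section 7 asks for it.

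The protocol already limits the damage in several ways:

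- Results are stratified by dosing interval, and no formal comparison of the strata is planned.
- Missed injections have a second summary, "The mean and median number of injections missed during a 12-month period", which is partly standardised for time.
- Cox regression for non-adherence uses time at risk.
- Early leavers are visible elsewhere in AIM 2, where discontinuation and its reasons are reported. Table 1 includes codes for non-adherence and for defaulting.
- Cumulative reports can be expected to show some growth in an ever-event proportion.

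These points stand, and they confine the concern without answering it. The 12-month summary covers missed injections only; for late injections the sole companion measure is the length of delay among those already late. The Cox model is specified to find associated factors, not to supply the reported level of adherence. Stratification leaves unequal follow-up within each stratum untouched.

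It would also go too far to say that early leavers are the least adherent and so bias the figure downwards. Table 1 lists many unrelated reasons for stopping, and an early leaver counts as adherent only if none of their injections was late or missed.

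**Conclusion.** The concern holds in limited form and merits a change. The two AIM 2 proportions measure adherence and opportunity together, because the formula has neither a horizon nor an exposure base.

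At an assumed independent 2% per injection, the same behaviour gives 38% under monthly and 22% under 2-monthly dosing at 24 months. The monthly figure is about 21% at an interim with evenly spread follow-up. Clustering would make these contrasts smaller. The interim and between-stratum readings are where the problem matters; at the final analysis, 8-16% discontinuation spread evenly changes the within-stratum figures little. Late injections are affected most, since they have no time- or opportunity-standardised summary at all.

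The direction of the effect follows from the formula. Its size rests on assumed values of q, k, the spread of follow-up and ρ, none of which the documents give. The precision tables in Section 8.4 are unaffected.

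**What to change.** In Section 8.7, AIM 2, within each dosing stratum:

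1. Replace the crude proportion as the main person-level estimate with a Kaplan-Meier estimate of time to first late injection, and likewise to first missed injection, at 6, 12 and 24 months, censored at discontinuation or last contact. This fixes the horizon and handles unequal follow-up.
2. Add late injections, and missed injections, divided by injections scheduled while on regimen, with a 95% confidence interval clustered by participant. This puts the two dosing intervals on a common footing, which the Kaplan-Meier estimate alone does not.
3. Keep the crude proportion, if wanted, as a labelled descriptive figure.

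The CAB+RPV LA regimen form in Annex 1 already has fields for scheduled date, dosing type, whether the injection was given and the actual date, so no new data items are needed. The cost is a wording change and slightly more programming. Censoring at discontinuation assumes that leavers would have resembled those who stay; the report should say so and show the discontinuation reasons alongside.

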# AIM 3. Assess the clinical effectiveness among PLWH who initiate CAB+RPV LA regimen

Given that this study involves PLWH in routine clinical care, and who may not attend clinic appointments at 6, 12 or 24 months, a window of 12 weeks around the date in question will be used for virologic failure. Thus, the proportion with virologic failure during first six months, at 6, 12 or 24 months  $\pm$  6 weeks will be used; and if none is available, the first measurement during first six months, after 6, 12 or 24 months (and at most 6 weeks after the measurement).

Proportion of participants who continue to be suppressed (VL of <50 copies/mL) at each time point (after 6, 12 and 24 months of follow up) will be estimated, as well as proportion of individuals with VL of <200 copies/mL. CD4 counts will also be assessed. The proportion of participants with virologic failure (2 consecutive HIV RNA VL  $\geq$ 200 copies/mL or one HIV RNA VL level  $\geq$ 200 copies/mL followed by a discontinuation of CAB+RPV LA regimen) will be estimated and time to failure will be assessed by the Kaplan-Meier method. The two-sided 95% associated confidence interval will be calculated with Kalbfleisch and Prentice's formula. Time to event will be defined as the time between the date of the initiation of CAB+RPV LA regimen and the date of virologic failure. Follow-up will be censored at the analysis time point, or the date of last study contact, or date of discontinuation of CAB+RPV LA regimen, or the date of lost to follow-up, whichever will occur first.

Genotypic resistance testing will be performed in participants with confirmed HIV RNA VL  $\geq$ 200 copies/mL. Resistance interpretation will be given using the Stanford algorithm (https://hivdb.stanford.edu/hivdb/by-mutations). All drug resistance mutations identified will be described and number and percentage indicated. The proportion of participants with genotypic resistance viruses among those with virological failure will be estimated by the number of participants with genotypic resistance viruses divided by the total number of participants with virological failure. The associated two-sided 95% exact (Clopper–Pearson) confidence intervals will be calculated. The frequency of viral subtype among those with virologic failure will be reported.

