#### **2.** Clinical effectiveness: assessed using the following measures:

- 1. Proportion of individuals, virologically suppressed/undetectable (<50 copies/mL) at 6,12 and 24 months following initiation of CAB+RPV LA regimen
- 2. Proportion of individuals with VL of  $<\!200$  copies/mL at 6,12 and 24 months following initiation of CAB+RPV LA regimen
- 3. Proportion of individuals with confirmed virologic failure (CVF) during the first 6 months, and at 6,12 and 24 months following initiation of CAB+RPV LA regimen defined as

- Two consecutive HIV RNA VL levels ≥200 copies/mL or
- One HIV RNA VL level \ge 200 copies/mL and regimen discontinuation within 4 months of VL \ge 200 copies/mL
- **3.** Resistance Testing: This is a non-interventional study aiming to capture SoC for PLWH in real world setting. Testing for resistance and subtype at virologic failure is part of SoC and the study will include only the clinical sites that follow the guidance for resistance testing.
  - Resistance testing along with subtype will be done for all participants with virologic failure during the 24 month follow-up period while on CAB+RPV LA
  - Resistance testing along with subtype will also be done during the 48 months following any switch from CAB+RPV LA in all participants with subsequent virologic failure on their new regimen(s) during the follow up period

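### The fallback for the 6-, 12- and 24-month viral-load window lies inside that window, and Aim 3 does not say whether the windowed or the Kaplan-Meier estimate is the reported failure proportion

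*Protocol*

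**What the plan says.** Protocol section 8.7, Aim 3, gives irregular clinic attendance as the reason for a window and states that "a window of 12 weeks around the date in question will be used for virologic failure". The next sentence sets the width at 6, 12 or 24 months plus or minus "6 weeks will be used; and if none is available, the first measurement during first six months, after 6, 12 or 24 months", and closes with a limit in brackets: "and at most 6 weeks after the measurement".

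The endpoint is set out in section 8.3.2 as "Proportion of individuals with confirmed virologic failure (CVF) during the first 6 months, and at 6,12 and 24 months". It is met by "Two consecutive HIV RNA VL levels" at or above 200 copies/mL, or by one such value with discontinuation of the regimen within 4 months. Aim 3 repeats the definition without the 4-month limit.

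The second paragraph of Aim 3 says that the proportion with failure "will be estimated and time to failure will be assessed by the Kaplan-Meier method". Time runs from initiation of the regimen to "and the date of virologic failure". Follow-up is censored at the earliest of the analysis time point, last contact, discontinuation or loss to follow-up. No window applies there. The proportions with VL <50 and <200 copies/mL at each time point are also planned in that paragraph, and the window sentence does not name them.

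**The concern.** There are two defects in one short paragraph.

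First, the fallback is there for participants who do not attend near the nominal month. A fallback helps only if it looks somewhere the main rule has not already looked, and this one appears to search part of the same interval again.

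Second, a visit window suits a status that can be read from one sample, such as VL <50. Confirmed failure is different: it needs two values, or one value and a stop, and it has a date. Asking who has failed in a 12-week window around month 24 is a different question from asking who has failed by month 24. The protocol plans an estimate of each kind and does not say which one answers Objective 3. The two can differ by an amount that matters against the precision the study was sized for.

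**Working it through.** **Inputs.** Window of 12 weeks in total, 6 either side of 6, 12 and 24 months (section 8.7, Aim 3). Fallback from the nominal month to at most 6 weeks later (same place, plain reading). Failure rate of 2% to 6% with N = 1000 and stated precision of 0.9 to 1.5 percentage points (section 8.4). Conversion: 1 month = 365.25/12/7 = 4.348 weeks, so 6, 12 and 24 months are weeks 26.1, 52.2 and 104.4.

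**The protocol's own figures.** 2 × 6 = 12 weeks, as stated. Exact Clopper-Pearson limits at N = 1000 are 1.23% to 3.07% for 2% and 4.61% to 7.66% for 6%. The half-widths are 0.9 and 1.5 points, as stated.

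**Step 1: does the fallback add anything?** With T the nominal week, the main window is [T − 6, T + 6] and the fallback is [T, T + 6].

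| Time point | Main window (weeks) | Fallback (weeks) | Fallback outside main window |
|---|---|---|---|
| 6 months | 20.1 to 32.1 | 26.1 to 32.1 | 0 weeks |
| 12 months | 46.2 to 58.2 | 52.2 to 58.2 | 0 weeks |
| 24 months | 98.4 to 110.4 | 104.4 to 110.4 | 0 weeks |

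The fallback is used only when the main window holds no value. Every value it could select would already be in the main window, so it selects none.

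**Step 2: is failure at a time point cumulative?** Sections 7 and 8.3.2 list failure during the first 6 months separately from failure at 6, 12 and 24 months. If failure at 6 months meant failure by 6 months, the two would be the same quantity. The wording for the time points is therefore not plainly cumulative, and the window sentence points to a snapshot.

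**Step 3: how much time lies between the windows?** Weeks 0 to 26.1 are covered by the first-six-months measure, and the month-6 window extends this to week 32.1.

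- Gap 1: 46.2 − 32.1 = 14.1 weeks.
- Gap 2: 98.4 − 58.2 = 40.2 weeks.
- Total: 14.1 + 40.2 = 54.3 of 104.4 weeks, or 52%.

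**Step 4: how many failures could be dated there?** The protocol gives no distribution of failure over time. Assume a constant hazard λ = −ln(1 − p)/104.4, where p is the 24-month cumulative failure and S(t) = exp(−λt). The expected number per 1000 in the gaps is 1000 × {[S(32.1) − S(46.2)] + [S(58.2) − S(98.4)]}.

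| p | Failures per 1000 by 24 months | Dated in the gaps | Share |
|---|---|---|---|
| 2% | 20 | 10.4 | 52% |
| 4% | 40 | 20.7 | 52% |
| 6% | 60 | 30.9 | 52% |

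At p = 2% the gap count is 1.0 point against a precision of 0.9; at p = 6% it is 3.1 points against 1.5. These are upper limits for the difference from this source under the assumption, because a participant still viraemic on treatment when a window opens could be counted there.

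**The case against.** The strongest reply is that failures between windows are already counted. The Kaplan-Meier analysis has no window, runs to the date of failure and is censored at the analysis time point, so it yields failure by 6, 12 and 24 months. That stands. A reader might infer that the study loses about half of its failures; the protocol does not support this. Only the windowed proportion is exposed. What remains is that the protocol does not say which estimate is reported.

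A second reply is that the bracketed limit is ambiguous, since "and at most 6 weeks after the measurement" has no clear anchor. If it meant after the end of the main window, the fallback would reach new ground (weeks 32.1 to 38.1 for month 6). The text does not say so, and it needs correcting on either reading. The sentence also repeats the first-six-months period within the fallback; I take that to belong to the separate period measure.

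A third reply concerns the denominator. A reader might infer that someone who fails at month 16 and stops is in neither the numerator nor the denominator at month 24, and that the windowed proportion is therefore a survivor estimate biased low. Section 8.7 does say that "The frequency and percentages (based on the non-missing sample size) of observed levels will be reported for all categorical variables", but this is a general rule for summaries. The same paragraph includes everyone who received a dose, Aims 2 and 4 use whole-group denominators where they write them out, and Aim 3 states none for the failure proportion. The window sentence does not require a value taken on the regimen, and participants who discontinue are followed for 48 months. If viraemic participants are tested more often, the error could even run upwards. Neither the exclusion nor the direction of bias is established.

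Finally, the gap count rests on an assumed hazard, and Aim 2 expects some participants with confirmed failure to remain on the regimen. That also stands, so the figures are given as a range and as conditional.

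**Conclusion.** The point holds in two parts. The fallback is void on its plain reading, by interval arithmetic that needs no assumption, and its anchor is unclear on any other reading. Separately, Aim 3 attaches a snapshot window to an event endpoint, plans an unwindowed Kaplan-Meier analysis beside it, and leaves open which gives the reported 6-, 12- and 24-month failure proportion.

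The uncovered time is 54.3 of 104.4 weeks. The 10 to 31 failures per 1000 depend on a constant hazard, on 24-month failure of 2% to 6%, and on no viraemia persisting into a later window. They measure how far one of two planned estimates could fall short of the other, not failures lost to the study. The protocol should be corrected here; the data needed for a sound estimate are already planned.

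**What to change.** Reword the window paragraph of Aim 3:

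- State that virologic failure by 6, 12 and 24 months is reported as the cumulative incidence from the Kaplan-Meier analysis already planned, using all viral loads, and drop the windowed failure proportion.
- Apply the plus or minus 6-week window to the VL <50 and VL <200 copies/mL proportions, which currently have no window.
- Give those proportions a fallback that reaches past the window and is anchored to the nominal month, for example the first viral load more than 6 and up to 12 weeks after it.

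The cost is one paragraph of rewording. No new data item is needed, because the case report form in Annex 1 already records dated viral loads and the date of discontinuation. The drawback is that fallback values lie further from the nominal month, so their number should be shown. At month 24 the example fallback runs to week 116.4, against 110.4 for the present window, so data extraction has to reach that far.

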#### 8.3.2. Outcome definitions

**Table 1.** Regimen discontinuation: Reasons for discontinuation as tabulated below will be collected for all participants switching off CAB+RPV LA regimen.

Code	Reason for Stopping Treatment
1	Treatment failure (i.e. virological, immunological, and/or clinical failure
1.1	Virological failure
1.2	Partial virological failure (multiple blips, low level viraemia)
1.3	Immunological failure - CD4 drop (25% or more)
1.4	Clinical progression
1.5	Resistance (based on test result)
2	Abnormal fat redistribution
3	Concern of cardiovascular disease
3.1	Dyslipidaemia
3.2	Cardiovascular disease
3.3	Weight gain
4	Hypersensitivity reaction (skin eruption etc.)
5	Toxicity, predominantly from abdomen/G-I tract
5.1	Toxicity - Liver
5.2	Toxicity - Pancreas
6	Toxicity, predominantly from nervous system
6.1	Toxicity - peripheral neuropathy
6.2	Toxicity - neuropsychiatric

6.3	Toxicity - headache
7	Toxicity, predominantly from kidneys
8	Toxicity, predominantly from endocrine system
8.1	Diabetes
9	Haematological toxicity (anemia etc.)
10	Hyperlactataemia/lactic acidosis
11	Bone toxicity
12	Social contra-indication
13	Contra-indication unspecified
14	Pregnancy - toxicity concerns (during pregnancy)
15	Pregnancy - switch to a more appropriate regimen for PMTCT
16	Death
17	Toxicity, unspecified
	Availability of more effective treatment (not specifically failure or side effect
18	related)
18.1	Simplified treatment available
18.2	Treatment too complex
19	Drug interaction
19.1	Drug interaction - commencing TB/BCG treatment
20	Injection fatigue (not related to safety)
21	Injection Site Reaction
22	Non-adherence
23	Drug not available
24	Other causes, not specified above
25	Lost to follow-up
26	Defaulter
27	Individual's wish/decision, not specified above
28	Physician decision to discontinue due to confirmed low level viremia (50-200)
29	Physician's decision, not specified above
99	Unknown

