#### 8.5. Data Collection

Following the approval of CAB LA and RPV LA, the study will collect follow up data prospectively on 1000 PLWH treated with the CAB+RPV LA regimen, for a follow-up period of 24 months. Participants who discontinue CAB+RPV LA regimen will be followed up for 48 months after switching to another ARV regimen. The NEAT ID Network coordinating center will receive data from the clinical sites per the protocol for the study. Detailed data collection form will be used to collect comprehensive data from clinical sites including dates of injections, clinical and laboratory parameters (virologic, immunologic, biochemistry, haematology and pathology), documented history of resistance at regimen initiation, resistance and HIV subtype data at virologic failure and after discontinuation and switching to another ARV regimen. Only clinical sites that, as SoC test all participants at virologic failure, for resistance and HIV subtype data and after discontinuation and switching to another ARV regimen will be included in the study.

In order to maintain confidentiality, the subject will be identified only by subject number. Subject data will be collected via extraction from individual medical record as source data by appropriately trained and authorised member(s) of the study team who must be identified and authorised in writing by the Principal Investigator (PI). A delegation of responsibility log will be updated accordingly.

Sites will provide / upload data every 6 months to the data management team who will store the data on a secure database with access to authorised personnel of the study management team only, maintained the log of authorised personnel by the sponsor representative.

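### The single-viral-load criterion for virologic failure has a 4-month limit in section 8.3.2 and none in section 8.7 (AIM 3), and AIM 3 leaves its failure date and its precedence over censoring unstated

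*Protocol*

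**What the plan says.** Protocol section 8.3.2, under clinical effectiveness, defines confirmed virologic failure by either of two routes. The first is "Two consecutive HIV RNA VL levels ≥200 copies/mL or". The second is one VL of at least 200 "and regimen discontinuation within 4 months of VL" at that level.

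Protocol section 8.7, AIM 3 does not refer back to that definition. It writes out its own in parentheses. The two-consecutive route is the same, but the second route is now one VL of at least 200 "copies/mL followed by a discontinuation of CAB+RPV LA regimen", with no limit on the interval.

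The same paragraph of AIM 3 measures time to event between "the date of the initiation of CAB+RPV LA regimen and the date of virologic failure". It censors at the earliest of the analysis time point, the last study contact, "or date of discontinuation of CAB+RPV LA regimen, or the date of lost to follow-up, whichever will occur first". It does not say whether failure by the second route is dated at the VL or at the stop, or what happens when an event and a censoring fall on the same day.

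**The concern.** The two sections describe one effectiveness outcome, and an analyst cannot follow both. Take a participant with a single VL of at least 200 at month 3 who re-suppresses and stops at month 20 for injection fatigue (code 20 in the discontinuation table). Section 8.3.2 says this is not a failure, because 17 months separate the VL from the stop. AIM 3 read literally says it is. The 4-month limit is what ties the stop to the viraemia. Without it, any later stop for any reason turns an old isolated VL into a failure.

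Section 8.4 expects 20 to 60 failures, so a few reclassified participants are visible. The same status feeds the failure proportion at each time point, the Kaplan-Meier curve, the Cox model for factors associated with failure, and the resistance proportion, whose denominator is everyone with virologic failure.

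The censoring rule raises a second, smaller question. Under the second route there is no failure until the participant stops, yet the stop is also listed as a censoring date. AIM 3 does not say which status prevails.

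**Working it through.** **1. The plan's own precision.** Exact Clopper-Pearson 95% limits with N = 1000 (Protocol 8.4):
- 20 failures (2%): 1.23% to 3.07%, half-width (3.07 − 1.23)/2 = 0.92 points.
- 60 failures (6%): 4.61% to 7.66%, half-width 1.52 points.

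These reproduce the stated 0.9 to 1.5. That table is not affected by this point.

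**2. Extra failures when the 4-month limit is dropped.**

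Inputs:
- Proportion q with an isolated VL of at least 200: not in the Protocol, assumed 2% to 5%.
- Proportion r stopping over 24 months: 8% to 16%. This is the range of the discontinuation table in 8.4. Reading it as a 24-month figure is an assumption, since 8.4 does not attach the range to a time.
- Time t of the isolated VL: assumed uniform over months 1 to 24.
- Stops: assumed unrelated to the VL, with constant hazard h = −ln(1 − r)/24.

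The wider wording adds participants who stop more than 4 months after the VL and before month 24, which is possible only for t between 1 and 20:

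extra per 1000 = 1000 × q × (1/23) × ∫ from 1 to 20 of [exp(−4h) − exp(−h(24 − t))] dt
= 1000 × q × {19·exp(−4h) − [exp(−4h) − exp(−23h)]/h} / 23.

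- r = 8%: h = 0.00347, exp(−4h) = 0.9862, exp(−23h) = 0.9232. The probability per isolated VL is 0.0263. With q = 2%, 20 × 0.0263 = 0.53 per 1000.
- r = 16%: h = 0.00726, exp(−4h) = 0.9714, exp(−23h) = 0.8461. The probability is 0.0529. With q = 5%, 50 × 0.0529 = 2.65 per 1000. A simulation of the same model gave 2.68.

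So the range is about 0.5 to 2.7 per 1000, or 0.05 to 0.27 percentage points:
- against 20 failures: 0.53/20 = 3% to 2.65/20 = 13%;
- against 60 failures: 0.53/60 = 1% to 2.68/60 = 4.5%.

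If 8-16% is instead a 12-month rate (h = −ln(1 − r)/12), the top of the range becomes 4.9 per 1000, or 0.49 points. That is still inside the half-width.

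**3. What the limit does.** Under the same model, unrelated stops within 4 months of the VL number 0.25 per 1000 at the low end and 1.31 at the high end, against 0.53 and 2.65 later. The limit therefore removes about two-thirds of coincidental failures: 0.53/(0.53 + 0.25) = 68% and 2.65/(2.65 + 1.31) = 67%.

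**4. Event against censoring, by choice of failure date.**
- Failure dated at the VL: the event precedes the stop, and nothing is lost.
- Failure dated at the stop: event and censoring tie. The usual Kaplan-Meier convention takes events before censorings at tied times, so again nothing is lost.
- Events disappear only if a completed failure is recoded as censored. For scale, if 10% or 25% of 40 failures qualified only by the second route (assumed shares), the count would fall to 36 or 30, that is from 4.0% to 3.6% or 3.0%. The Protocol does not instruct this.

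**The case against.** The case for leaving this alone has weight. Section 8.3.2 is headed as the place for outcome definitions and can be read as governing, with AIM 3 as a loose summary. The numerical effect lies within the planned confidence interval, no hypothesis is tested, and the isolated-VL rate has no source in the Protocol. Event dating and ties are ordinary matters for a statistical analysis plan. On size and on censoring this largely stands. It does not remove the contradiction, because AIM 3 states a complete definition for the analysis and does not cross-refer.

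A reader might infer more from these sections, and four stronger readings are not supported:

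- *The censoring rule deletes second-route failures.* That would require recoding a completed event as censored, which the text does not say.
- *One-sixth of on-regimen time (4/24 = 17%) cannot be classified, because follow-up is "for a follow-up period of 24 months".* That is exposure time, not a share of events. Only participants with an unconfirmed VL of at least 200 in the last 4 months are affected: at the assumed 2-5%, 20 × 4/23 = 3.5 to 50 × 4/23 = 8.7 per 1000. Participants who discontinue are followed for 48 months after switching. Incomplete confirmation near the end of fixed follow-up is ordinary administrative truncation.
- *Stops for low-level viraemia are failures censored informatively.* Code 28, "Physician decision to discontinue due to confirmed low level viremia (50-200"), lies below the endpoint threshold apart from its boundary value, so these participants are non-failures by design.
- *Stops for partial virological failure or resistance (codes 1.2, 1.5) are missed.* With a VL of at least 200 in the preceding 4 months they already count under 8.3.2, whatever the reason code.

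**Conclusion.** The definition in AIM 3 is wrong as written, because it contradicts 8.3.2 on the main effectiveness outcome. Followed literally, it counts late, unrelated stops as virologic failures. The expected size is about 0.5 to 2.7 extra failures per 1000. It rests on an assumed 2-5% isolated-VL rate, 8-16% stopping over 24 months, a constant hazard and stops independent of the VL. The case for correcting it is the contradiction and the negligible cost, not the size of the shift.

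The censoring point holds only as an ambiguity. The failure date for the second route and its precedence over censoring are unstated, and one sentence settles both. Severity: should be fixed.

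**What to change.** In Protocol section 8.7, AIM 3:

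1. Replace the parenthetical definition with a reference to 8.3.2, or repeat it in full with the 4-month limit.
2. Date failure at the qualifying VL of at least 200: the first of the two values for the consecutive route, and the single value for the discontinuation route.
3. State that a discontinuation completing the second route is an event and not a censoring.

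The cost is a wording amendment. The case report form already records viral-load dates and the date and reason of discontinuation, so no new data are needed. Neither further chart extraction beyond month 24 nor an added sensitivity table by reason code is called for on this point.
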